**VERSION DATE: February 7, 2019** 

### **1.0 Purpose of the Study:**

Approximately 10-15% of the 9 million adults with severe mental illnesses (SMI) are employed, which is associated with reduced psychological distress. However, the employment rate increases to  $\sim 30\%$  in adults with SMI enrolled in Supported Employment (SE) (i.e., the gold standard for vocational training). A recent model of SE shows that active job-seeking behavior (e.g., completing job interviews) is an essential treatment target for employment, and finding a job is moderated by self-efficacy and anxiety about interviewing. Moreover, these targets are underdeveloped as adults with SMI have poor interviewing skills and want training to alleviate their fears and poor self-efficacy related to interviewing7-14. Currently, SE relies on role-play training led by "Employment Specialist" counselors to enhance interview skills, but SE clients reported that this method did not improve their skills. In response, NIMH funded the development of Virtual Reality Job Interview Training (VR) and evaluation of VR efficacy in a series of randomized controlled trials (RCTs, R44 MH080496). The results suggest that VR hit the targets by improving interview skills and self-efficacy in several cohorts with SMI  and demonstrated efficacy by increasing the likelihood of getting job offers. Of note, the integration of new technologies into SE is a top research priority for SE developers. Thus, VR is an ideal intervention to evaluate as an effective enhancement to SE. Thus, there are a series of critical next steps to test if VR is effective at improving vocational outcomes for SE clients with SMI. A first step will test if replacing SE interview training with VR enhances person-level (e.g., higher employment rate) and b) system-level (e.g., staff efficiency and costeffectiveness) SE outcomes. A second step will evaluate the initial implementation of VR within SE, while a third step will evaluate potential mechanisms for enhanced SE outcomes.

Our long-term goals are to develop, evaluate, and implement virtual reality interventions that enhance vocational recovery from SMI. The objectives of this application are to: 1) evaluate if VR enhances SE outcomes and if the benefits of VR generalize to improved social skills and reduced psychological distress; and 2) identify facilitators and barriers associated with large-scale implementation of VR. **Our central hypothesis is that VR will enhance vocational outcomes in a SE program.** This hypothesis is based on our research showing that VR performance predicted greater odds of receiving a job offer and a shorter duration until receiving a job offer, and recommendations from a community advisory board of SE leaders and staff. We also recognize that VR needs research to maximize the effectiveness of VR in real-world settings.

In this application we propose to conduct a single-blinded confirmatory effectiveness RCT (and a process evaluation) of VR by comparing subjects receiving SE with VR (instead of clinician role-plays) (SE+VR) to subjects receiving SE as usual (SE Only). Subjects will include adults with SMI who are newly enrolled in SE at Thresholds, the largest community mental health service provider in Chicago. We are well prepared to conduct this study because our team has extensive experience with community-based vocational and implementation research, and in leading prior studies at Thresholds. The Specific Aims are:

**1.** Evaluate if SE+VR, compared to SE Only, enhances SE outcomes for adults with SMI. At a personlevel, we *hypothesize (H)* that SE+VR subjects, compared to SE Only subjects, will have higher employment rates (*H1*), greater improvement in job interview skills (*H2*), get jobs sooner (*H3*), and have reduced psychological distress (*H4*) by 6-month follow-up. At a system-level, we hypothesize that SE+VR will be more cost-effective than SE Only (*H5*). Exploratory Subaims: 1. Explore if VR generalizes to social skills by testing if VR training relates to enhanced social skills and longer job tenure for clients (person-level) and if SE staff spend fewer hours coaching communication at work (systems-level); 2. Explore if SE+VR staff have increased efficiency (e.g., time spent helping clients with applications and networking with employers(system-level)). **2.** Evaluate mechanisms of employment outcomes and psychological distress. Based on Corbiere's model, we *hypothesize* is that interview skills, measured independently during role-play, will mediate the effect of interview training on employment outcomes (*H*6). Exploratory Subaims: **1.** Explore if post-training levels of interviewing anxiety/self-efficacy mediate the relationship between VR training and interviewing skills and if this mediation is moderated by pre-training levels of anxiety and self-efficacy (Fig 1b); **2.** Explore if employment outcomes mediate the relationship between interviewing skills and psychological distress at 6-month follow-up.

**3.** Conduct a multilevel, multidisciplinary, and mixed-method process evaluation of VR adoption and implementation to assess the acceptability, scalability, generalizability, and affordability of VR. We will use focus groups and interviews (with clients, staff, and leaders) to identify facilitators and barriers to implementing VR. We will use budget impact analysis to estimate the cost of implementing VR at Thresholds.

### 2.0 Background / Literature Review / Rationale for the study:

More than 9 million Americans have severe mental illnesses (e.g., major depression, bipolar disorder, and schizophrenia) with long periods of clinical stability when they can work. A primary aim for adults recovering from SMI is getting a job as 70% of this population wants to work, and employment increases quality of life. Thus, adults with SMI, service providers, and policy makers view a return to work as a critical milestone for recovery. However, only 10-15% of this group is employed and struggling to find jobs increases their psychological distress.

The field's gold standard vocational program for adults with SMI is Supported Employment (SE), which uses staff-based role-plays to train interview skills. However, despite their desire to improve interview skills only 30% of SE clients reported this method was helpful. Also, SE clients were more likely to get a job if SE staff were present during interviews. Thus, SE job interview training methods may be limited, which is a major barrier for this group to get a competitive job offer.

Based on the need to enhance interview skills, NIMH funded the development and evaluation of Virtual Reality Job Interview Training (VR) in a series of RCT efficacy studies (R44 MH080496). Briefly, VR overcomes the limitations of SE interview training by using behavioral learning principles that facilitate sustainable changes in behavior. VR improved interview skills in a lab setting and demonstrated efficacy (increased likelihood of attaining a job offer and getting job offers sooner) for four independent groups of adults with SMI. Moving forward we will evaluate VR in the community at Thresholds, which is the largest SE provider in Chicago and offers a standardized version of SE called *Individual Placement and Support (IPS)*. Although IPS strives for rapid job placement, it devotes much less attention to job interview training, which is a limitation to IPS given that "competitive" jobs require interviews.

Replacing typical IPS staff-led interview role-play training with VR could enhance IPS person-level and systemlevel employment outcomes. Moreover, VR could generalize to better person-level (e.g., social interactions, job tenure) and system-level (e.g., fewer hours spent coaching communication at work) employment outcomes, which we will explore. The improvement in these outcomes would demonstrate that VR has more than an incremental impact on employment outcomes. The effectiveness of IPS interview training has never been evaluated, and as such, this study will gain critical knowledge. We will test if VR enhances interview skills beyond the effects of IPS, and test if VR contributes to person-level and system-level employment outcomes. **IPS and SE are synonymous within this protocol.**  Lastly, prior studies evaluated the implementation of IPS; however, the implementation of enhancements to IPS (e.g., VR) have yet to be studied. Thus, we propose to use the Consolidated Framework for Implementation Research (CFIR) to guide a process evaluation of VR. The CFIR organizes implementation into several domains, and we will focus on the CFIR's process domain (i.e., is an intervention being used and delivered as designed) to evaluate the 1) agency's plan to implement VR, 2) scalability of VR, and 3) client, staff, and leader views on a) barriers and facilitators to implementing VR, b) whether VR is used as designed, and c) suggested refinements. Hence, this study will gain critical knowledge by evaluating the cost effectiveness of VR and how VR fits into the system-level workflow, service structure, and billing of Thresholds to provide essential data for agencies that might consider adopting VR.

### 3.0 Inclusion and exclusion criteria:

# We will recruit 180 IPS clients at Thresholds diagnosed with a mental disorder with or without psychotic features into the randomized controlled trial. *Inclusion/exclusion criteria are outlined below:*

Inclusion Criteria: 1) Over 18 years old;

2a) all chronic schizophrenia spectrum disorders, including schizophrenia, schizoaffective disorder, delusional disorder, brief psychotic disorder, schizophreniform disorder, other specified schizophrenia spectrum and related disorder, and unspecified schizophrenia spectrum and related disorders;

2b) all bipolar spectrum disorders beyond bipolar type I and II to include cyclothymia, other specified bipolar and related disorder, and unspecified bipolar and related disorders;

2c) all depressive disorders, including disruptive mood dysregulation disorder, major depressive disorder, persistent depressive disorder, other specified depressive disorder, and unspecified depressive disorder;2d) post traumatic stress disorder

3) fluency in English; 4) at least a 4th grade reading level; 5) enrolled in IPS; 6) active IPS enrollee as indicated by at least 1 contacts with his/her Employment Specialist in the past 30 days; 7) currently unemployed or underemployed; 8) Planning to go on interviews within 4 weeks of enrolling in the study; 9) willing to be video recorded; and 10) willing and able to provide informed consent. We will review each participant's medical record to confirm his/her mental health history.

Exclusion Criteria: 1) documented developmental or learning disability; 2) medical condition that may compromise cognition (e.g., Parkinson's Disease, Alzheimer's Disease, Huntington's Chorea, Moderate or Greater TBI); 3) uncorrected vision or hearing problems; 4) active suicidal ideation within the last 30 days with at least some intent to act, with or without a specific plan; this would be reflected in a score of 4 or 5 on the Suicidal Ideation section of the Columbia Suicide Severity Rating Scale (CSSRS); and 5) a past suicide attempt within the past 30 days that did not include preparatory acts or behavior, but was defined by a potentially self-injurious act committed with at least some wish to die as a result of the act.

We will not include any special populations: adults unable to consent; minors; infants; childrens; teenagers (ages 17 and younger); or prisoners.

Notably, clients will self-report their intention to go on interviews. We will over-select female clients so that they represent ~40% (n=60) of our sample.

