## D. 3. Combined Baseline Visit 2/3 for Thresholds' Clients (completed at Northwestern University or at Threshold's location) will require participants to complete:

1. Employment History Interview (EHI) The EHI will assess competitive work history data: length of time since last full-time (or any) employment, number of days employed in the past 5 years, history of prior interview training, and number of job interviews completed in the past three months. The EHI will also assess current housing status, income, and criminal justice history.

2. Brief Psychiatric Rating Scale (BPRS) (lasting approximately 30 minutes). The BPRS will assess psychiatric symptoms including somatic concern, anxiety, emotional withdrawal, conceptual disorganization, guilt feelings, tension, mannerisms and posturing, grandiosity, depressive mood, hostility, suspiciousness, hallucinatory behavior, motor retardation, uncooperativeness, unusual thought content, blunted affect, excitement, and disorientation.

3. The Beck Depression Inventory (approximately 15 minutes) is a self-report of depression symptoms.

A rating of "2 ("I would like to kill myself," or 3 ("I would kill myself if I had the chance" on item 9 on the Beck Depression Inventory indicates presence of suicidal ideation.

When a participant meets one of the above cutoff scores, the research staff will administer the **Columbia-Suicide Severity Rating Scale (C-SSRS).** A total score of 4 or higher on the "Intensity of Ideation" section of this measure will indicate whether or not the participant has a level of suicidal risk that requires further consideration. The procedures outlined in section 10 (Risks to Participants) will be followed if a participant scores 4 or higher.

4. MATRICS Consensus Cognitive Battery (MCCB) (approximately 1 hour) . The MCCB is a standardized cognitive battery for use with adults with schizophrenia and related disorders.

5. Participants will receive a break and be provided a healthy snack.

6. WHO Quality of Life-BREF (WHOQOL-BREF) (approximately 10 minutes) . The WHOQOL-BREF is a brief quality of life survey.

7. The 12-item Short Form Health Survey (SF-12) (approximately 10 minutes) . This assessment is a brief survey about the participant's physical health.

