Alternatively, if participants are unable to attend visit 10 and/or 11 in person, the study team will schedule a series of brief phone calls in order to collect the self-reported study data by phone. In addition, the study team will offer participants the opportunity to complete their follow-up role-play assessment by means of a videoconference through BlueJeans. The BlueJeans videoconference will then be recorded by the University of Michigan research team that is approved for this study and the recordings will be stored using the previously approved methods for storing audiovisual data.

Alternatively, if the participants do not want to complete the videoconference then the participants will be offered the opportunity to complete their follow-up role-play assessment by means of a teleconference through BlueJeans. The BlueJeans teleconference will then be recorded by the University of Michigan research team that is approved for this study and the recordings will be stored using the previously approved methods for storing audiovisual data.

**D. 9. Monthly Check-in Telephone Calls for Thresholds Clients (completed via telephone) will be a repeat of procedures of the Monthly Check-in Telephone Calls for Thresholds Clients (see D. 8.).** These calls will be scheduled at monthly intervals after completion of the 6-month follow-up until the 9-month follow-up (see D. 11.), for a total of 2 calls.

D. 10. The 9-Month Follow-Up for Thresholds Clients (completed via telephone) will include only the Follow-up Employment History interview that will assess how many job interviews were completed, total hours worked, how many jobs were offered (and accepted), hourly wage, type of job, jobs terminated (and why).

The 9-Month Follow-Up Telephone Call will last approximately 10 minutes. If participants complete at least one of the two check-in calls between the 6-Month and 9-Month Follow-Up calls, they will be paid \$10 by Thresholds after the completion of the 9-Month Follow-Up call.

**D. 11. Participation Complete.** If a Thresholds client becomes employed prior to the 6-month follow-up call, they will still participate in monthly check-in phone calls and the 6-month follow-up. Their participation in the study will then be complete after completing the 6 month visit.

If the participant becomes employed between the 6- and 9-month follow-up calls, the participant will be asked additional questions on their next check-in call, which will be their last check-in.

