Data Analysis Plan for Aims 1 & 2. In this intent-to-treat study, we will collect data on 160 subjects. The biostatistician will monitor the data for distribution normality and transform abnormally distributed variables if needed. Correction for Multiple Comparisons: To minimize spurious findings, we will adjust the 3 primary tests using a false discovery rate at 0.05 (see below). Covariates: Although randomization should protect against group differences, we will covary for any between-group differences that are observed regarding demographic, cognitive, clinical and vocational history, booster sessions, and the number of completed interviews. Missing Data: We will follow the intent-to-treat principle and in longitudinal analyses we will use multiple imputation models to analyze the data in the presence of missing data. Data processing and cleaning will occur during the study, including checking for missing data and inconsistencies. All videos will be stored on the project's secure server. A Data Safety and Monitoring Board will monitor for adverse events (see 15.0 below).

**Hypothesis 1:** IPS+VR trainees will have higher employment rates than IPS Only by T3. **To test H1**, we will use multiple logistic regression and a Wald Chi-square test of the coefficient to its standard error, to compare the adjusted employment proportions in the two conditions (attained a job=1 vs. failed to attain a job or censored with a job=0, between T1 and T3). We calculated power using simulation in R, correcting for small samples and multiple testing with false discovery rate for the 4 primary tests (our power analysis is conservative, relying on Bonferroni corrections for all tests). Accounting for 10% missing, our trial that recruits 80 subjects in each arm has 80% power for a two-sided 0.05/4=.0125 level test when the OR = 3.2, with IPS+VR effectively doubling the

rate from 25% to 53% employment. Based on our earlier study where we found an OR of 8.7, or effectively tripling the employment rate from 25% to 75%, and a power of 0.99 at this magnitude of effect, we feel confident that we will have sufficient power in this study.

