**Hypothesis 2:** IPS+VR trainees will have greater improvement in *job interview skills* than IPS Only by T2. **To test H2**, we will conduct a repeated measures analysis of variance (RM-ANOVA) with pre and post interview scores as the repeated measures and treatment group as the fixed factor. Based on our pilot data, we expect r=.7 between T1 and T2 scores, and an effect size of d=.67 between pre and post interview role-play scores using VR. Assuming a small-to-moderate effect within IPS Only (e.g., d=.25), our best power estimate assumes a medium effect size contrasting IPS Only with IPS+VR (d=.67-.25=.42). This effect size and correlation imply an expected 6.9% reduction in within subject error for the treatment–x-time effect. Thus, 80 subjects at .0125 level will yield 82% power to detect this effect. For the ANOVA model, 160 subjects will be sufficient to detect a reduction of within subject error of 4.7% with 80% power. Assuming a full sample effect size of d=.46 (.67+.25)/2), this reduction in error corresponds to an effect size of d=.62 for the IPS+VR group and d=.30 in the IPS only group (a difference of d=.32).

**Hypothesis 3:** IPS+VR will get jobs sooner than IPS only by T3. **To test H3**, we will use a Cox proportional (or non-proportional) hazards regression model to assess the adjusted hazard rate on time-to-employment for IPS+VR vs. IPS Only, adjusting for potential covariates (e.g., completed training trials). For a power analysis for **H3**, we assume a constant hazard rate for the distribution of time-to-employment in both groups. We also assume that a proportion of 0.20 of the subjects in the IPS Only group will find a job by T3 (that is, a hazard rate of 0.0085 for IPS Only). This analysis is estimated based on limited pilot data and log-rank power tables. Thus, 160 subjects provide 80% power for a 0.0125-level test comparing time-to-employment in the two arms to detect a hazard rate of 2.0 for IPS+VR vs. IPS Only.

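### Underemployed clients are eligible, but H1, H3 and H5 do not say how a job already held at entry is treated, and baseline job status is adjusted for only if an imbalance is observed

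*Combined protocol and SAP*

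**What the plan says.** **Eligibility.** Inclusion criterion 7 in section 3.0 admits clients who are "currently unemployed or underemployed". Underemployment is not defined, and no expected share or cap is given. Criterion 8 requires every client to be planning job interviews within four weeks.

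**H1 (section 14.0).** The outcome is coded "attained a job=1 vs. failed to attain a job or censored with a job=0, between T1 and T3". The same paragraph introduces the hypothesis as a comparison of employment rates by T3 and describes the test as one of employment proportions.

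**H3 (section 14.0).** The outcome is time to employment. The power statement assumes that a proportion of 0.20 of IPS Only clients "will find a job by T3". No event or time zero is given for a client who is working at entry.

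**H5 (section 14.0).** The denominator of the cost-effectiveness ratio is the between-arm difference in job attainment, with no further definition.

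**Follow-up (section 4.0, D.11).** Completion rules turn on becoming employed: "If a Thresholds client becomes employed prior to the 6-month follow-up call", participation ends after the 6-month visit. Clients who do not find employment continue to 9 months.

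**Baseline data and randomization.** The Employment History Interview (section 4.0, D.3) records "length of time since last full-time (or any) employment" before randomization. Randomization (D.4) uses blocks of six with no stratification factor. Under the covariate rule in section 14.0, vocational history is adjusted for only when a group difference appears.

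**The concern.** On its ordinary meaning, an underemployed client has some work already. The plan never says what happens to that job in the three analyses that use employment. Two careful analysts could code the same client differently in H1, and for H3 they would have to invent a rule.

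Three things are at stake. First, a job that predates randomization cannot be an effect of the training. Scoring it as a success would add the same constant to both arms and shrink the difference. Second, even when only new jobs count, a client with some work and a client with none may find new jobs at different rates. Leaving that factor to an imbalance check makes the adjusted model depend on the data. Third, the D.11 rules do not fit an underemployed client, so it is unclear whether follow-up for that client ends at 6 or 9 months.

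**Working it through.** **1. What the text settles, and what it leaves open**

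| Analysis | Points to new jobs only | Leaves it open |
|---|---|---|
| H1 | The coding asks for a job attained between T1 and T3 | The hypothesis and test are worded as employment rates and proportions. T1 and T3 are not defined there. The clause on clients censored with a job can be read in two ways |
| H3 | The power assumption speaks of finding a job | The event and time zero are not stated for someone already working |
| H5 | Attainment suggests a gain | No definition |
| D.11 | Becoming employed suggests a change of state | A client already working fits none of the groups |

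**2. Reproducing the plan's H1 power**

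Inputs, all from section 14.0, Hypothesis 1:
- "Accounting for 10% missing, our trial that recruits 80 subjects in each arm", which gives 80 × 0.90 = 72 evaluable per arm.
- "80% power for a two-sided 0.05/4=.0125 level test when the OR = 3.2". The critical value is z = 2.498.
- "rate from 25% to 53% employment". An odds ratio of 3.2 from 25% gives 51.6%, while 53% corresponds to 3.38, so both are carried.

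The log-odds Wald power is Φ(|log OR|/SE − z), with SE = √[1/(72·pc(1−pc)) + 1/(72·pt(1−pt))].
- 25% vs 53%: log OR 1.219, SE 0.360, power Φ(0.885) = 81%. The pooled two-proportion formula gives 84%.
- 25% vs 51.6%: log OR 1.163, SE 0.360, power 77%. The pooled formula gives 79.3%.

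The stated 80% is therefore reproduced.

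**3. Conditional check: held jobs scored as successes**

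This scoring rule is not in the documents. Let f be the share of each arm holding a job at entry, also not in the documents and so shown as a range. Each rate becomes p′ = f + (1−f)p, and the difference shrinks by the factor (1−f).

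At f = 10%, starting from 53%: pc = 0.10 + 0.90 × 0.25 = 0.325 and pt = 0.10 + 0.90 × 0.53 = 0.577. The difference is 0.252, log OR 1.041, SE 0.347, and power is Φ(0.506) = 69%.

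| Assumed f | Rates from 53% | Power, Wald / pooled | Rates from 51.6% | Power, Wald / pooled |
|---|---|---|---|---|
| 0 | 25.0 vs 53.0 | 81% / 84% | 25.0 vs 51.6 | 77% / 79% |
| 5% | 28.75 vs 55.35 | 75% / 78% | 28.75 vs 54.0 | 71% / 73% |
| 10% | 32.5 vs 57.7 | 69% / 71% | 32.5 vs 56.5 | 64% / 66% |
| 20% | 40.0 vs 62.4 | 57% / 58% | 40.0 vs 61.3 | 51% / 52% |
| 30% | 47.5 vs 67.1 | 45% / 45% | 47.5 vs 66.1 | 40% / 40% |

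**4. The new-job rule**

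If only jobs started after randomization count, and underemployed clients find them at the planned rates, then p′ = p. Power stays in the f = 0 row and there is no dilution.

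**5. Analysis limited to clients with no job at entry**

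At 25% vs 53% with the pooled formula, n per arm is 72(1−f), or 64.8, 57.6 and 50.4 at f = 10%, 20% and 30%. Power is 79%, 73% and 66%. Such an analysis is useful as support but should not replace the full comparison.

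**The case against.** The strongest reply is that the plan already means new jobs. A job held before T1 was not attained between T1 and T3, and randomization follows directly on the pre-training role-plays, so little time can fall between T1 and allocation. Criterion 8 makes every client an active job seeker, so an underemployed client is at risk of attaining a new job. The baseline interview takes work history and follow-up records jobs offered and accepted, so old and new jobs can be told apart. Randomization also makes the unadjusted comparison valid whatever the mix of job status.

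Most of this stands, and it rules out two stronger readings. A reader might infer that the H1 outcome is diluted by pre-existing jobs. The documents do not support that: nowhere do they say that held jobs count, and the H1 coding points the other way. A reader might also infer that the plan gives a wrong answer whichever way such a client is scored. It does not: counting only new jobs is a sound rule, and nothing in the documents shows that underemployed clients find new jobs at a rate different from the 25% (H1) or 20% (H3) assumed for IPS Only.

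What the reply does not remove is the missing rule. H1 carries two descriptions, H3 has no event or origin for a working client, and being able to separate old from new jobs is not an instruction to do so. Nor does the validity of an unadjusted test justify choosing a covariate after seeing whether the arms differ on it.

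**Conclusion.** The concern holds as a gap in definition and as an avoidable data-driven covariate rule. It does not hold as a demonstrated loss of power or bias. The employment event needs a stated rule for clients with a job at entry, most clearly in H3 but also in H1 and H5, and D.11 should match it.

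The fall to about 64-71% power at a 10% share, or 51-58% at 20%, rests on two things the documents do not supply: a rule that scores held jobs as successes, and the share of underemployed clients. Under the new-job rule with equal rates the loss is zero. That baseline job status is prognostic is a reasonable assumption, not something the documents show. The case for pre-specifying it is that it is known before randomization and costs almost nothing.

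**What to change.** - In section 14.0, under H1, H3 and H5, state that the event is the first new job started after randomization, that time zero is randomization, and that a job already held does not count. Word the H1 hypothesis to match its coding.
- Define underemployed in section 3.0 and record a baseline flag (no job / underemployed) from the eligibility check and the Employment History Interview.
- Pre-specify that flag as a covariate in the H1 logistic model and as a stratum in the H3 Cox model, whether or not an imbalance is seen.
- Add a sensitivity analysis in clients with no job at randomization.
- Reconcile the completion wording in section 4.0, D.11 with the same event, so that it is clear how it applies to a client already working.

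The cost is protocol and SAP wording and one more model term. The information is already collected before randomization, so no extra clients or visits are needed. The changes should be made before outcome data are analysed by arm.
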